3.0 Specific Aims

Hypotheses:

- •Topical sodium nitrite cream, at 2% concentration, is safe and well tolerated when applied for an extended period of time (10 weeks) in patients with sickle cell disease and leg ulcers.
- •Topical sodium nitrite accelerates healing of skin ulcers and decreases ulcer relatedpain compared to placebo in patients with sickle cell disease and leg ulcers.

Specific Aims:

- To determine the safety and tolerability of prolonged (10 weeks), twice a week application of topical sodium nitrite in patients with sickle cell disease and leg ulcers
- To determine if topical sodium nitrite accelerates wound healing as defined by >25% improvement over placebo arm
- •To determine if topical sodium nitrite decreases pain at the wound site >20% over placebo

Secondary Objectives:

- To evaluate the effect of hydroxyurea on leg ulcer's healing in combination with topical sodium nitrite or placebo
- To assess changes in ulcer microbiome after application of sodium nitriteor placebo and how they may relate to rate of healing
- •To evaluate the dermal composition and microvascular structure in the ulcer's biopsy of subjects enrolled on this study.

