5.1 Study Design and Methods

5.2 Overview

This will be randomized, placebo controlled, double blinded study

We plan to enroll fifty subjects with homozygous sickle cell disease (HbSS), sickle-thalassemia (Hb S-ß thalassemia), HbSC, HbSD, or HbSO^{Arab}, in order to have 40 subjects complete at least 8 weeks of treatment, after an expected 20% dropout.

Subjects will receive 2% topical sodium nitrite cream twice a week for 10 weeks or placebo with vehicle only.

Subjects will have 0.1 cm of 2% sodium nitrite cream or placebo cream applied per 1 cm² of the total ulcerated area. If a subject has more than one ulcer, all of them will be treated with either "study cream" or placebo. Areas will be rounded to the nearest 1 cm². If a subject has more than one ulcer and the total sum of all of them is above 100 cm², then one of the ulcers can be enrolled

PI: [name]

^{*} If a patient does not qualify because he/she has an infection at the time of enrollment or at run-in, he/she can initiate the protocol two weeks after the infection has been cleared.

in the study, as long as it does not exceed the 100 cm² size. The other wounds will continue standard of care only. The total amount of sodium nitrite administered to each subject will vary depending upon the size of the ulcer but the treated total surface area will not exceed 100 cm² (i.e., subjects will receive a maximum of 10 cm of sodium nitrite cream).

Administration of study cream or placebo will be double blinded. The pharmacist will not be blinded, so he/she will be aware of who is receiving the investigational drug for safety purposes.

Randomization:

Randomization will be stratified by use of hydroxyurea to minimize its potential confounding effect on the study outcomes; we expect that 50% of participants use hydroxyurea. In addition, within each stratum (use or non-use), random treatment assignment will be balanced, i.e., 1:1 allocation, within blocks. This type of stratified block-randomized allocations will be generated by the study statistician applying a computer algorithm. The randomized allocation will occur once a subject is determined to be eligible for participation after the screening visit and the run in phase, but prior to the first cream application.

Un-blinding Procedures:

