PI: [name] Version 5 in order to assess cutaneous vascularization (i.e., angiogenesis), inflammation (tissue II-6, TGF- \Box , etc.), and markers of neurogenic inflammation³⁶.

At the end of 10 weeks of treatment, subjects that still have an open ulcer will be offered continuation of care at Montefiore or University of Pittsburg or referred back to the community.

Subjects will be followed off treatment but on study with monthly visits for an additional six months to evaluate the long term effect of topical sodium nitrite on the host and the ulcer (how many ulcers re-open or close). These visits will consist of measurement of all wounds by light photography and a detailed history of intervening ulcer treatments. If patients cannot return to the hospital or have moved away, we will call them and obtain the information on the phone and ask for a photograph. The photo can be obtained by the patient him or herself. Thereafter, they will be followed up with phone calls once a year for a total of 2 years, to establish whether this therapy is changing the natural history of ulcers in this population.

Rationale for the selection of subjects' number and endpoints

Sample size: We plan to randomize a total of 50 subjects to sample size of 20 completers per arm (40 subjects total) after an anticipated 20% dropout rate is taken into account. This sample size is determined based on feasibility of recruitment within the budget constraint and time frame of the study; we anticipate enrolling 1~2 eligible subjects per month. Although the focus of analysis will be more on estimation of treatment effect sizes and their 95% confidence intervals, the anticipated sample size is adequate to detect 88% vs. 48% response rate, as defined by >25% reduction of ulcer size from baseline, between treatment and control groups, with >80% at a two-sided significance level of 0.05 (see table 1). We note that in the Phase 1 study we observed an 88% response rate. Therefore, our study will be adequately powered if response rate in the placebo group is smaller than 48%.

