Week 2-10/ Visits 4-22: The subjects will be seen twice a week for cream application, wound care and monitoring of side effects. The wound will be measured once a week manually by the wound care nurse and measured by photography after 10±2 applications. Blood pressure and vital signs will be measured upon arrival to outpatient unit and 30 minutes±10 minutes after the application of the study cream, unless clinically indicated. If the blood pressure is stable after cream application for all visit 4, 5, 6, post cream application blood pressure monitoring wound not be needed for future study visits. The wound will be cleaned and study cream will be applied.

Routine bloods will be drawn as clinically indicated. A research methemoglobin level will be obtained every other week.

A repeat pregnancy test will be performed at week 4 in women of reproductive age. Pain assessment: a VAS scale will be obtained with each application of the study cream. If there is more than one ulcer, individual VAS scale per ulcer will be obtained.

After the first three subjects have completed the first application of the study drug, if there are no significant side effects, especially significant changes in BP, patients will be offered the option of applying the second weekly dose of the cream at home, by themselves or by a home health nurse. We will dispense the exact amount of cream to be applied eachweek. This will reduce the number of visits to the wound care / hospital location to once a week.

End of study: Subjects will return the week after the last application to have the study cream removed and for end of study procedures. Blood pressure and vital signs will be measured with a pulse oximeter. The surface area of all ulcerated surfaces will be measured and photographed with defined lighting, distance, exposure, and camera. The wound doctor or nurse will remove the "study cream" and obtain a repeat microbiome sample. A VAS scale will be obtained to assess pain. If there is more than one ulcer, individual VAS scales will be obtained per ulcer. ASCQ-ME, PROMIS, BDI, and BPI surveys will be distributed to the patient. Study labs will be obtained (see Appendix 1). Patients who discontinue the study will still receive end of study procedures.

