7.2 Stopping Rules

The study medication will be stopped if the subject experiences healing of the ulcer.

Subjects will be removed from therapy should one or more of the following occur:

- If any methemoglobin reading is >7.5%, the research study cream will be discontinued.
- Investigator or patient considers discontinuation of the study to be in the patient's best interest.
- Clinically significant hypotension (decrease in the systolic BP >20mmHg from the baseline systolic BP and of 10mmHg from the baseline diastolic BP application, and symptomatic dizziness, tachycardia, or hypoxia as per the judgment of the PI).
 - A dose will be skipped if the subject has a systolic blood pressure of ≤80mmHg and/or a diastolic blood pressure of ≤50mmHg, once the blood pressure has been checked with a repeat blood pressure check. If three doses are skipped in a row for this reason, the subject will be removed from therapy.
- Sustained pulse oxygen saturation below 85% for >15 minutes while on supplemental oxygen (up to 4L by NC).

- Increased ulcer pain requiring increased opioid use by 50%.
- Development of osteomyelitis or other systemic infection while on therapy.
- Lack of compliance, as measured by missing more than two sequential cream applications and/or at the PI's discretion.

Rules for Stopping the Study:

- Occurrence of severe toxicities:
 - Three subjects requiring sodium nitrite cream discontinuation
 - Death while on protocol, if it is attributable to the sodium nitrite cream

8. **Analysis of the Study**

We will first review and summarize data using descriptive summaries and graphical analyses to ensure recorded values are within appropriate ranges, in order to check for outliers and abnormal values. We will explore the success of randomization by comparing groups on potential confounding variables, and will include variables that are not equally distributed between groups in multivariable models. For primary analyses, we will adhere to the intent-totreat analysis principle that assigns groups as randomized as opposed to actually treated. For sensitivity analyses, we will conduct as-treated analysis and use incomplete data as well after imputation of missing data due to early dropouts; imputation methods such as last-observationcarried-forward or MCMC will be conducted and results from thereof will be compared.

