8.1 Primary Endpoints and Analysis

The primary endpoint of this phase II study will be the assessment of tolerability and occurrence of adverse effects of topical sodium nitrite compared to placebo.

- 8.1.1 Frequency of each adverse event will also be tabulated. To compare the safety of prolonged (10 weeks) treatments between the experimental/treatment and usual care/placebo groups, we will apply a non-parametric Mann-Whitney test on the number of adverse events.
- 8.1.2 Effect sizes of the treatment on the ulcer size reduction will be determined by differences in response rates or odds-ratios, and the 95% Cl's will accordingly be To test if topical sodium nitrite accelerates wound healing, as defined by >25% improvement over placebo arm, we will apply a Chi-square test. Logistic regression models will be applied if inclusion of confounding variables deems necessary. We will also test if declines of weeklymeasured absolute ulcer size on a continuous scale over the study period will be different between the two groups by applying mixed effects linear models for analysis of repeatedmeasure outcomes.
- 8.1.3 Effect sizes of the treatment on the pain reduction will be determined by differences in response rates or odds-ratios, and the 95% CI's will accordingly be estimated. To test if topical sodium nitrite decreases pain at the wound site >20% over placebo, we will apply a Chisquare test. Logistic regression models will be applied if inclusion of confounding variables deems necessary. We will also test if declines of weekly-measured absolute pain VAS scores on a continuous scale over the study period will be different between the two groups by applying mixed effects linear models for analysis of repeated-measure outcomes.

25

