PI: [name] Version 5 62/077,622, filed on November 10, 2014, entitled "TOPICAL SODIUM NITRITE FORMULATION," and PCT Patent Application No. PCT/US2015/060015, filed on November 10, 2015, entitled "TOPICAL SODIUM NITRITE FORMULATION," has six inventors: [name], [name], [name], [name], [name], and [name], who were all NIH employees at the time of invention.

- Or. [name] is presently employed on the faculty of the University of Pittsburgh.
- oDr. [name] is presently employed on the faculty of the Albert Einstein College of Medicine.

12 Adverse Events Reporting

The Principal Investigator (or a physician member of the research team) and the study coordinator will assess each participant for any new or continuing adverse events. An adverse event is defined as any untoward medical occurrence in a subject of a clinical investigation that involves the administration of a pharmaceutical product. The event need not to have a causal relationship with the treatment. This includes any events that are not seen at baseline or, if present at baseline, have worsened in severity. These adverse events will only be collected during study treatment time. The severity and drug relationship will be determined, and any management required will be recorded. The investigator will review the clinical laboratory test results in a timely fashion. Only those results qualifying as adverse events, as defined above, will be recorded as an adverse event.

Table 2. Expected Adverse Events Possibly Related to Study Drug						
Severe stinging and burning sensation, requiring an increase in narcotic use.						
Peripheral vasodilation with hypotension (BP below 85/50, or symptomatic						
dizziness, tachycardia, or hypoxia as per the judgment of the PI)						
Methemoglobinemia >7.5%						

Acute chest syndrome Angioedema Angioedema Aplastic crisis Aplastic crisis/anemia Aplastic crisis/anemia Appendicitis Bone Infarction Cardiomegaly Cerebrovascular accident Cholecystitis, hepatic sequestration Cranial nerve palsy Decreased kidney function Decreased lung function Pever Renal Insufficiency/albuminuria Headache Hematuria Hematuria Reticulocytosis (10%-20%) Hemiplegia Hemolysis Hepatosplenomegaly Hyperplastic bone marrow Hyposthenuria Increase Jaundice Metabolic acidosis	Table 3. Expected Adverse Events Re	elated to Sickle Cell Disease

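### The only test named for the primary safety endpoint counts adverse events without regard to time observed, which can differ by arm through healing or dropout

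*Combined protocol and SAP*

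**What the plan says.** Section 8.1 makes tolerability and adverse effects against placebo the primary endpoint. Section 8.1.1 tabulates each AE and then, "To compare the safety of prolonged (10 weeks) treatments" between arms, says "we will apply a non-parametric Mann-Whitney test on the number of adverse events". It names no rate, denominator, offset or effect size. Sections 8.1.2 and 8.1.3, on ulcer size and pain, do provide effect sizes with 95% CIs.

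Three other statements bear on how long a subject is observed:

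- Section 7.2: "The study medication will be stopped if the subject experiences healing of the ulcer".
- Section 12: "These adverse events will only be collected during study treatment time". The term is not defined.
- Section 5.2 plans enrolment "in order to have 40 subjects complete at least 8 weeks of treatment, after an expected 20% dropout".

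Section 3.0 states the hypothesis that would make the arms differ: "Topical sodium nitrite accelerates healing of skin ulcers".

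**The concern.** A raw count depends on both the event rate and the time over which events could be recorded. A rank test on counts compares the arms fairly only if that time is alike in both.

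If AE recording stops when the cream stops, a subject who heals at week 5 contributes half the planned time. If more subjects heal on active, as the trial hopes, the active arm shows fewer AEs even when its weekly rate equals that on placebo. A real excess on active is then partly hidden. Dropout can distort the count in the same way, towards whichever arm loses more time. This affects the between-arm comparison that the plan declares primary.

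**Working it through.** **The plan's own figures.** None is given for the AE comparison. The only power statement (88% v 48% ulcer response, 20 completers per arm, above 80%) reproduces at 79.7% by normal approximation and 82.1% by exact enumeration of the chi-square test. It has no bearing on safety.

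**When does AE collection end?** The passages point both ways.

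- *Fixed 10 weeks.* The schedule header treats weeks 1-10 as one blinded treatment phase. Section 8.1.1 speaks of 10 weeks. Section 5.3 says of weeks 2-10 "The subjects will be seen twice a week for cream application, wound care and monitoring of side effects", with no exception for healed subjects. Section 5.2 keeps the off-treatment label for what comes after week 10: "Subjects will be followed off treatment but on study with monthly visits for an additional six months".
- *Each subject's own time on cream.* Section 7.2 ends the cream at healing. Section 5.2 brings the final quality-of-life form forward to healing if that comes first. Section 5.3 places the end-of-study visit one week after the last application, which for a healed subject may be well before week 10.

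No passage settles it.

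**Inputs.** From the plan: 50 randomised 1:1, so 25 per arm; 10 weeks of treatment; dropout 0.20 x 50 = 10 subjects. The plan gives no AE rate, healing time or dispersion for this trial, so these are assumed: 0.3-0.6 AEs per week and dispersion 0.5-3.3. Phase 1 (section 2.4) offers only a rough guide to dispersion, (variance - mean)/mean². In the seven subjects at 1.8% and 2.0%, diastolic blood pressure events numbered 5, 3, 6, 2, 0, 0, 0: mean 2.286, variance 6.238, dispersion (6.238 - 2.286)/2.286² = 0.76. Over all 18 subjects: mean 0.889, variance 3.516, dispersion 3.3. These are counts of one event type over 4 weeks, not of all AEs, so they are illustrative only.

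**Exposure.** Mean weeks observed = 10 - (share stopping early) x (10 - stop week). With equal weekly rates, the ratio of mean counts equals the ratio of mean weeks.

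**Simulation.** Gamma-Poisson counts with equal true weekly rates, tested by two-sided 5% Mann-Whitney (nominal 2.5% in each direction; Monte Carlo error about 0.2-0.4 points in the healing rows).

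| Scenario, active v placebo | Mean weeks | Ratio | False finding |
|---|---|---|---|
| 20% v 5% healed, week 8 | 9.6 v 9.9 | 0.970 | active safer 2.8-3.5% |
| 4 v 1 healed, week 5 | 9.2 v 9.8 | 0.939 | active safer 3.0-4.5% |
| 20% v 5% healed, week 5 | 9.0 v 9.75 | 0.923 | active safer 3.1-5.2% |
| 9 v 1 healed, week 5 (unfavourable) | 8.2 v 9.8 | 0.837 | active safer 4.4-11.4% |
| 5 v 5 healed, week 5 | 9.0 v 9.0 | 1.000 | active safer 1.9-2.5% |
| Common window, everyone followed, 4 v 1 or 9 v 1 healed | 10 v 10 | 1.000 | 2.2-2.7% each way |
| 10-week window, 8 v 2 lost at week 5 | 8.4 v 9.6 | 0.875 | active safer 3.5-7.4% |
| 10-week window, 2 v 8 lost at week 5 | 9.6 v 8.4 | 1.143 | active worse 3.6-7.1% |

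The last two rows split the expected 10 dropouts unevenly and assume no AE data after dropout. A fixed window alone therefore does not remove the problem.

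**Does a rate analysis help?** Assume 43% v 10% healing at weeks 3-8, 0.3 AEs per week and dispersion 0.5 (2,000 replicates, error up to about 1 point). The 43% is 3 of 7 closures at 1.8% and 2.0% in phase 1; the 10% is a guess. With collection ending at healing, mean weeks are 8.05 v 9.55, a ratio of 0.84.

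- Equal true rates: Mann-Whitney finds active safer in 8.3% of trials and worse in 0.6%. A rate ratio using time observed, with robust standard errors, gives 2.5% and 2.9%.
- Fixed window with 30% v 10% unfollowed dropout: Mann-Whitney finds active safer in 6.9%. With 10% v 30% it finds active worse in 6.6%. The rate ratio stays at 2.4-3.3% in each direction.
- True on-cream rate ratio 1.5, no dropout: harm is detected in 9.5% (Mann-Whitney, collection ending with cream), 22.3% (Mann-Whitney, fixed window) and 33.8% (rate ratio, collection ending with cream).

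**The case against.** The best defence is that a fixed 10-week window is the more natural reading. If everyone is followed through it, the Mann-Whitney test holds its nominal error. Even on the other reading, modest healing differences move 2.5% only to about 3-5%. AE tabulation, stopping rules and the DSMB do not depend on this test. All of that stands.

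It does not close the point. The plan never says that AE collection continues after healing or dropout. Subjects who discontinue get end-of-study procedures (5.3), but further AE contact is not mentioned. Subjects on cream are seen up to twice weekly, so less frequent questioning after healing could bring back part of the bias inside a nominal fixed window. The as-treated and imputation analyses in section 8 are sensitivity analyses; the imputation is for early dropouts, and neither clearly covers stopping for healing.

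Two supporting arguments are weak and are not relied on. The absence of an AE row in the schedule means little, since sections 5.3 and 12 already require AE assessment. The emphasis on effect sizes and 95% CIs in section 5.2 sits in the ulcer-response sample-size paragraph, so extending it to safety is an interpretation.

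**Conclusion.** The point holds as a cheap improvement, with medium confidence. The count test is biased whenever time observed differs by arm, and the plan leaves that possible. The sizes, about 3-5% for modest healing differences and about 4-11% in the unfavourable case, apply only if collection ends with the cream, and they rest on assumed AE rates, stop times and dispersion. Loss of AE data after unequal dropout is a separate route that a fixed window does not block, and it can act in either direction.

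A reader might infer more than the documents support:

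- *That the plan ends AE collection at healing.* It does not say so, and several passages lean the other way.
- *That phase 1 closures (2 of 3 at 2.0%, 1 of 4 at 1.8%) imply a large bias.* Seven subjects without a placebo arm cannot establish a between-arm healing difference.
- *That subjects are left unprotected, or that a decision would be wrong.* No decision rule rests on this p-value.
- *That Mann-Whitney must be dropped.* It is sound when observation is equal, but it should not stand alone.

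**What to change.** 1. In section 12, state that AEs are collected from first application to the planned end-of-study visit after week 10, for every randomised subject who can be followed, whether or not cream has stopped, with the same AE questions at the same planned times in both arms. Reconcile this with section 5.4, which takes subjects with a dose-limiting toxicity out of the protocol, so that it is clear whether their AE follow-up continues.
2. In section 8.1.1, add as a planned analysis, not an optional one, the AE rate per subject-week observed in each arm and the rate ratio with 95% CI (negative binomial or quasi-Poisson, log time observed as offset). Keep the Mann-Whitney test alongside.
3. Report weeks observed, weeks on cream and on-treatment AEs by arm.

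The cost is a few sentences, plus brief extra AE contacts for early stoppers if a fixed window was not already intended. The downside is dilution: AEs after cream stops weaken a drug effect that ends with the cream. With 9 v 1 healers and a true on-cream rate ratio of 1.5, Mann-Whitney power over a common window is 6-27% if the excess ends with the cream, against 7-36% if it persists. That is why on-treatment AEs are shown separately.

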During the abovementioned phase 1 trial of topical sodium nitrite, we observed no SAE's. We documented a grade 1 decrease in diastolic blood pressure below 50 mmHg, judged as possibly related to study drug 16 times in 4 participants. Of the four participants, two enrolled in Cohort 4, the highest concentration of the drug (2.0% sodium nitrite cream) and the other two enrolled into Cohort 3.a (1.8% sodium nitrite cream). The participants had fluctuating diastolic blood pressure measurements that occasionally reached below 50 mmHg even **before study cream application**; therefore, the association with study cream application is unclear. All events resolved spontaneously within an hour (i.e., at the next BP check).

15

PI: [name] Version 5

Experiments in rats showed that methemoglobin levels peaked at 45-50 min after application of 30 g/L sodium nitrite solutions on abraded skin³². Percutaneous absorption of a solution differs from the absorption rate from Aquaphor (the vehicle in our current preparation) and it seems to be slower than that from solution. There was no evidence of accumulation either, as predicted by our pharmacokinetic models^{34,35}.

In the proposed phase 2 trial we plan to answer this toxicity question, since we will be treating patients blindly with a placebo preparation and we will be able to ascertain whether the fluctuations in BP are intrinsic to this patient population, their frequent use of opioids, and/or chronic wide pulse pressure.

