The medical monitor may request unblinding to attribute toxicities if a serious adverse event occurs to determine attribution, or if a dose limiting toxicity occurs to determine if placebo or active treatment was used.

A run in period of at least 2 weeks will be conducted, during which patients will receive/optimize wound care at the Center that will enroll the subjects, following standard of care, routinely available therapies. Patients that experience a reduction of their wound size by >25% during this time will be excluded from the trial, as this suggests an effect secondary to improved wound care only. These patients will remain on protocol and their wound will be measured monthly for up to 6 months or until closure, whichever comes first. If a subject develops an acute vaso-occlusive episode and is hospitalized during the run in period, he/she will have the run in period extended in order to allow the subject to be safely discharged from the hospital and return to outpatient care.

Close monitoring of VSS, especially BP, will be done, to assess changes in patients receiving study cream, compared to placebo.

Measurements of all leg ulcers and photographs will be obtained at the following points: At Baseline

After the 2 weeks run in period, to determine eligibility for study cream application
At mid-point: after 10 applications of study cream, to determine the need for drug modification
At end of study: after the last application of the study cream

An accurate assessment of pain will be obtained each time that size measurements are obtained.

Quality of life questionnaire (ASCQ-Me) will be given before initial application and at the end of protocol or when the ulcer(s) is (are) healed, whatever comes first.

We will monitor metHb level as a safety measure, despite the fact that the phase 1 study did not show significant elevations of metHb. **Teratogenicity** is not a consideration, since the phase 1 study demonstrated minimal systemic absorption of nitrite and nitrate, therefore the risk for the gonads and potential offspring is limited to nonexistent.

Among the entry studies to be obtained, a **3-4 mm skin optional biopsy** may be performed at the edge of the ulcerated area. If the patient has multiple ulcers, the surgeon/wound care expert will decide which one is the safest to biopsy. This will be done

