7.1 Monitoring of Subjects and Criteria for Withdrawalof Subjects

Monitoring: The safety of topical sodium nitrite will be closely monitored. Vital signs will be obtained before application and post-application at hours 1, 2, 3, 4, 5. If no decrease in systolic blood pressure is detected (clinically significant hypotension: see Section 7.1), patients will be discharged home.

The primary expected toxicity is low grade, asymptomatic methemoglobinemia. Therefore, a blood sample for methemoglobin safety measurement will be obtained after the first application, then weekly.

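### The primary safety analysis gives no by-arm estimate for methemoglobin or blood pressure, the two toxicities the protocol singles out

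*Combined protocol and SAP*

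**What the plan says.** Section 8.1 sets the endpoint: "The primary endpoint of this phase II study will be the assessment of tolerability and occurrence of adverse effects of topical sodium nitrite compared to" the control cream. Section 8.1.1 then provides two outputs. One is descriptive: "Frequency of each adverse event will also be tabulated". The other is the only between-arm safety test: "we will apply a non-parametric Mann-Whitney test on the number of adverse events". The response rates, odds ratios, 95% intervals and repeated-measures mixed models in Sections 8.1.2 and 8.1.3 are for ulcer size and pain only.

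Elsewhere the protocol is specific about what it expects the cream to do:

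- Section 7.1: "The primary expected toxicity is low grade, asymptomatic methemoglobinemia".
- Section 2.4.2, on the phase 1 falls in diastolic pressure, says that with a placebo arm "we will be able to ascertain whether the fluctuations in BP are intrinsic to this patient population".
- Section 5.2 says blood pressure will be watched closely "to assess changes in patients receiving study cream, compared to placebo". It names no measure, time point or method.

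Section 12 defines an AE openly, as any untoward medical occurrence that is new or worse than at baseline. It says of laboratory results: "Only those results qualifying as adverse events, as defined above, will be recorded as an adverse event". Table 2, the list of expected events possibly related to the drug, has the entry "Methemoglobinemia >7.5"% for methemoglobin, and hypotension as pressure below 85/50 or symptoms.

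**The concern.** The endpoint and its analysis are poorly matched. Methemoglobin and blood pressure are measured as numbers on a schedule, but the plan analyses neither as a number. They reach the primary analysis only if someone records them as AEs.

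For methemoglobin, the toxicity expected is low grade and without symptoms, which is the kind least likely to be recorded. For blood pressure, events are added to all other AEs in a population for which Table 3 lists several dozen expected disease-related events. The safety comparison could therefore say little about the two effects the protocol asks about, although the data to estimate them will be available.

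**Working it through.** **The plan's own figure.** There is no power or precision statement for safety. The only one, in Section 5.2, concerns healing: 88% against 48% with 20 per arm, two-sided 0.05, power above 80%. Exact enumeration of the uncorrected chi-square test gives 82.1%, so it reproduces, but it does not bear on this point.

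**Inputs from the documents.** 50 randomized 1:1, so 25 per arm, or 20 per arm completing (Section 5.2). Phase 1 maximum methemoglobin 4.1%, in one of 18 subjects (Sections 2.4 and 5.2). Phase 1 diastolic falls below 50 mmHg: 16 events in 4 participants, or 16/4 = 4 each, all in the 1.8% and 2.0% cohorts. Table 1 of Section 2.4 shows four and three ulcers in those cohorts, so 4 of 7, or 57%, if one ulcer per subject was treated.

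**Methemoglobin.**

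1. No phase 1 reading reached the Table 2 level: 4.1% is below 7.5%.
2. Illustration (assumptions: baseline mean 1.5%, SD 1.0 percentage point, normal values). A 1.0-point rise moves the mean to 2.5%. The Table 2 level is then (7.5 − 2.5)/1.0 = 5 SD away, and the chance that a reading exceeds it is about 3 in 10 million. The rise would add essentially no Table 2 methemoglobin events.
3. A direct two-sample t comparison of a shift of 0.8 to 1.0 SD has 79–93% power with 25 per arm and 69–87% with 20.
4. The 95% interval has half-width t × √(2/n) in SD units: 2.011 × √(2/25) = 0.57 with 25 per arm, and 2.024 × √(2/20) = 0.64 with 20.

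**Blood pressure, count test.** Simulation with 25 per arm. Background AEs are negative binomial with shape 2 (assumption; the documents give no rate). Each affected subject adds one or four hypotension events, and the Mann-Whitney test is applied to the totals. Repeat runs differ by one or two points.

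| Hypotension, active vs placebo | Events per affected subject | Background mean | Power |
|---|---|---|---|
| 40% vs 5% | 1 | 1 to 4 | about 20% down to 6% |
| 40% vs 5% | 4 | 1 to 4 | about 56% down to 28% |
| 57% vs 5% | 4 | 1 | about 89% |
| 57% vs 5% | 4 | 2 | about 80% |
| 57% vs 5% | 4 | 4 | about 53% |

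**Blood pressure, subjects affected.** Exact power of Fisher's test on the number of subjects with hypotension, 25 per arm, 40% on active:

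| Placebo incidence | 5% | 10% | 15% | 20% | 25% |
|---|---|---|---|---|---|
| Power | 82% | 59% | 38% | 23% | 13% |

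The direct comparison is clearly better when hypotension on placebo is rare, and weak when it is common. Sections 2.4 and 2.4.2 report diastolic readings below 50 mmHg before application in phase 1, so the right-hand columns cannot be dismissed. This favours analysing the change in pressure from before to after application, which removes each subject's starting level.

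**The case against.** Several stronger readings are tempting, and the documents do not support them.

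- A reader might infer that the primary analysis cannot show either toxicity. That is wrong for blood pressure. Hypotension is a named Table 2 event and would have its own line in the AE table, and phase 1 recorded low diastolic pressure as an AE. Section 5.2 also states an intent to compare with placebo; what is missing is the method.
- A reader might take 7.5% as the floor for recording methemoglobin. It is an entry in a list of expected events. The sentence on laboratory results points back to the open AE definition, which bars no lower value. That a low-grade rise would go unrecorded is a likelihood, not a rule. It is supported by Section 2.4, which treats the 4.1% reading as within safety thresholds.
- A reader might infer that a non-significant count test will be taken as proof of safety. The documents never say so. Individual and study stopping rules (Section 7.2) and review of all AEs by the monitoring board (Section 13) also bear on safety. Section 5.2 says the analysis will emphasise effect sizes and intervals, although Section 8.1.1 does not carry that over to safety.

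Two further points stand. The count test can do well when events are frequent, repeated and set against little background. And a small asymptomatic methemoglobin rise may be clinically acceptable: Section 9.3 reports 5.7% in volunteers without adverse events. Whether a rise is acceptable and how large it is are separate questions, and only an estimate answers the second.

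**Conclusion.** The concern holds as a mismatch between the stated safety questions and the planned analysis. Section 8.1.1 has an AE table and a count test, and no by-arm estimate or interval for methemoglobin or blood pressure values. The count test is insensitive to a low-grade methemoglobin rise and dilutes a blood pressure signal.

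The size of the dilution depends on assumptions that the documents cannot settle: background AE rate, events per affected subject and placebo incidence. Across the settings shown, power of the count test runs from about 6% to about 89%. The advantage of comparing subjects affected runs from large to slight as placebo incidence rises, so the 82% figure should not be quoted alone.

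This should be corrected before unblinding, because it concerns the primary endpoint. It does not undermine the design or the data collection.

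**What to change.** Add to Section 8.1.1:

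1. The between-arm difference in post-application methemoglobin with 95% confidence interval, adjusted for hydroxyurea stratum and for pre-treatment methemoglobin where a contemporaneous value exists. A footnote to the schedule of procedures waives the repeat when documented normal results are available, so the screening value may be an old chart result.
2. The between-arm difference in change from before to after application in systolic, diastolic and mean pressure at the first application, by mixed model with 95% interval. Section 5.3 schedules readings at hours 1 to 5 for every subject at that visit, whereas later post-application readings may lapse after visit 6.
3. The proportion of subjects with each Table 2 event, with risk difference and exact or score 95% interval.

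Keep the count test as supportive, and base the safety statement on the intervals.

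The following should also be reconciled, since they determine what is measured and counted: the methemoglobin schedule (every other week in Section 5.3, weekly in Section 7.1, and screening, visit 3 and two later columns in the schedule table); the methemoglobin limits (above 7% in Section 5.4, above 7.5% in Section 7.2 and Table 2); and the definitions of hypotension in Section 7.2 and Table 2.

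The additions to Section 8.1.1 cost analysis text and a few tables, with no new visits, samples or subjects. The downside is more safety estimates to report, each with modest precision. With 0 of 25 subjects affected, the upper 95% limit is still 1 − 0.025^(1/25) = 13.7%, and no change of analysis alters that.
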